## 1.0 TRIAL SUMMARY

[figure not shown]
Abbreviated Title	Pembro-XL888
Trial Phase	Phase I
Clinical Indication	GI Malignancies
Trial Type	Single arm dose escalation
Type of control	None
Route of administration	IV and PO
Trial Blinding	None
Treatment Groups	Pembrolizumab and XL888
Number of trial subjects	38-50
Estimated enrollment period	12 Months
Estimated duration of trial	14 months
Duration of Participation	6 months
Estimated average length of treatment per patient	6 months

## 2.0 TRIAL DESIGN

Open label phase I trial. Primary objective is to determine the recommended phase 2 dose (RP2D) of the combination of XL888 and pembrolizumab. The design is 3+3 with 3 dose levels of XL888 (X). MTD is defined as the dose at which less than one-third of the subjects experience a DLT in the first 4 weeks of treatment.

After determining the RP2D, an additional 16 patients with pancreatic cancer (Arm A) and 16 patients with colorectal cancer (Arm B) will be enrolled in an expansion phase to confirm toxicity profile and obtain paired biopsies. Paired biopsy performed on 8 patients in each group. Patient selected for biopsy must have a primary or metastatic non-bone site that is amenable to safe biopsy. Bone only lesions are not suitable for biopsy. Patients undergoing paired biopsies will be assigned into two treatment cohorts (8 in each) and treated according to the schema below.

## 2.1 Trial Diagram

## 3.0 OBJECTIVE(S) & HYPOTHESES

### 3.1 Primary Objective & Hypothesis

- (1) **Objective: Determine the recommended phase II dose for the combination of XL888 and pembrolizumab**

**Hypothesis:** The combination of a PD-1 inhibitor with HSP90 inhibitor is safe with no added toxicity.

### 3.2 Secondary Objectives & Hypotheses

- (1) **Objective:**

**A. Define the toxicity profile of the combination of XL888 and pembrolizumab.** The additional patients enrolled on the expansion cohorts will help confirm the toxicity profile.

- B. Evaluate the activity of the combination of XL888 and pembrolizumab in previously treated patients with gastrointestinal tumors. Specifically, we will measure response rate, response duration and progression free survival. This will only be preliminary data since this is a secondary objective.**

### **3.3 Exploratory Objective**

**Objective: Evaluate the effect of the combination on the immune profile in the serum and in tumor biopsies.**

**Hypothesis:** The HSP90 inhibitor will change the micro-environment to favor an immune response to the PD-1 inhibitor.

## **4.0 BACKGROUND & RATIONALE**

### **4.1 Background**

Refer to the Investigator's Brochure (IB)/approved labeling for detailed background information on MK-3475 and XL888.

#### **4.1.1 Pharmaceutical and Therapeutic Background- Pembrolizumab**

The importance of intact immune surveillance in controlling outgrowth of neoplastic transformation has been known for decades. Accumulating evidence shows a correlation between tumor-infiltrating lymphocytes (TILs) in cancer tissue and favorable prognosis in various malignancies. In particular, the presence of CD8+ T-cells and the ratio of CD8+ effector T-cells / FoxP3+ regulatory T-cells seems to correlate with improved prognosis and long-term survival in many solid tumors.

The PD-1 receptor-ligand interaction is a major pathway hijacked by tumors to suppress immune control. The normal function of PD-1, expressed on the cell surface of activated T-cells under healthy conditions, is to down-modulate unwanted or excessive immune responses, including autoimmune reactions. PD-1 (encoded by the gene *Pdcd1*) is an Ig superfamily member related to CD28 and CTLA-4 which has been shown to negatively regulate antigen receptor signaling upon engagement of its ligands (PD-L1 and/or PD-L2). The structure of murine PD-1 has been resolved. PD-1 and family members are type I transmembrane glycoproteins containing an Ig Variable-type (V-type) domain responsible for ligand binding and a cytoplasmic tail which is responsible for the binding of signaling molecules. The cytoplasmic tail of PD-1 contains 2 tyrosine-based signaling motifs, an immunoreceptor tyrosine-based inhibition motif (ITIM) and an immunoreceptor tyrosine-based switch motif (ITSM). Following T-cell stimulation, PD-1 recruits the tyrosine phosphatases SHP-1 and SHP-2 to the ITSM motif within its cytoplasmic tail, leading to the dephosphorylation of effector molecules such as CD3 $\zeta$ , PKC $\theta$  and ZAP70 which are involved in the CD3 T-cell signaling cascade. The mechanism by which PD-1 down modulates T-cell responses is similar to, but distinct from that of CTLA-4 as both molecules regulate an overlapping set of signaling proteins. PD-1 was shown to be expressed on activated lymphocytes including peripheral

CD4+ and CD8+ T-cells, B-cells, T regs and Natural Killer cells. Expression has also been shown during thymic development on CD4-CD8- (double negative) T-cells as well as subsets of macrophages and dendritic cells. The ligands for PD-1 (PD-L1 and PD-L2) are constitutively expressed or can be induced in a variety of cell types, including non-hematopoietic tissues as well as in various tumors. Both ligands are type I transmembrane receptors containing both IgV- and IgC-like domains in the extracellular region and contain short cytoplasmic regions with no known signaling motifs. Binding of either PD-1 ligand to PD-1 inhibits T-cell activation triggered through the T-cell receptor. PD-L1 is expressed at low levels on various non-hematopoietic tissues, most notably on vascular endothelium, whereas PD-L2 protein is only detectably expressed on antigen-presenting cells found in lymphoid tissue or chronic inflammatory environments. PD-L2 is thought to control immune T-cell activation in lymphoid organs, whereas PD-L1 serves to dampen unwarranted T-cell function in peripheral tissues. Although healthy organs express little (if any) PD-L1, a variety of cancers were demonstrated to express abundant levels of this T-cell inhibitor. PD-1 has been suggested to regulate tumor-specific T-cell expansion in subjects with melanoma (MEL). This suggests that the PD-1/PD-L1 pathway plays a critical role in tumor immune evasion and should be considered as an attractive target for therapeutic intervention.

Pembrolizumab is a potent and highly selective humanized monoclonal antibody (mAb) of the IgG4/kappa isotype designed to directly block the interaction between PD-1 and its ligands, PD-L1 and PD-L2. Keytruda™ (pembrolizumab) has recently been approved in the United States for the treatment of patients with unresectable or metastatic melanoma and disease progression following ipilimumab and, if BRAF V600 mutation positive, a BRAF inhibitor.

### **Rationale for pembrolizumab dose selection/regimen/modification**

An open-label Phase I trial (Protocol 001) was conducted to evaluate the safety and clinical activity of single agent MK-3475. The dose escalation portion of this trial evaluated three dose levels, 1 mg/kg, 3 mg/kg, and 10 mg/kg, administered every 2 weeks (Q2W) in subjects with advanced solid tumors. All three dose levels were well tolerated and no dose-limiting toxicities were observed. This first in human study of MK-3475 showed evidence of target engagement and objective evidence of tumor size reduction at all dose levels (1 mg/kg, 3 mg/kg and 10 mg/kg Q2W). No MTD has been identified to date. 10.0 mg/kg Q2W, the highest dose tested in PN001, was the dose and schedule utilized in Cohorts A, B, C and D of this protocol to test for initial tumor activity. Recent data from other clinical studies within the MK-3475 program has shown that a lower dose of MK-3475 and a less frequent schedule may be sufficient for target engagement and clinical activity.

PK data analysis of MK-3475 administered Q2W and Q3W showed slow systemic clearance, limited volume of distribution, and a long half-life (refer to IB). Pharmacodynamic data (IL-2 release assay) suggested that peripheral target engagement is durable (>21 days). This early PK and pharmacodynamic data provides scientific rationale for testing a Q2W and Q3W dosing schedule.

A population pharmacokinetic analysis has been performed using serum concentration time data from 476 patients. Within the resulting population PK model, clearance and volume parameters of MK-3475 were found to be dependent on body weight. The relationship between clearance and body weight, with an allometric exponent of 0.59, is within the range observed for other antibodies and would support both body weight normalized dosing or a fixed dose across all body weights. MK-3475 has been found to have a wide therapeutic range based on the melanoma indication. The differences in exposure for a 200 mg fixed dose regimen relative to a 2 mg/kg Q3W body weight based regimen are anticipated to remain well within the established exposure margins of 0.5 – 5.0 for MK-3475 in the melanoma indication. The exposure margins are based on the notion of similar efficacy and safety in melanoma at 10 mg/kg Q3W vs. the proposed dose regimen of 2 mg/kg Q3W (i.e. 5-fold higher dose and exposure). The population PK evaluation revealed that there was no significant impact of tumor burden on exposure. In addition, exposure was similar between the NSCLC and melanoma indications. Therefore, there are no anticipated changes in exposure between different indication settings.

The rationale for further exploration of 2 mg/kg and comparable doses of pembrolizumab in solid tumors is based on: 1) similar efficacy and safety of pembrolizumab when dosed at either 2 mg/kg or 10 mg/kg Q3W in melanoma patients, 2) the flat exposure-response relationships of pembrolizumab for both efficacy and safety in the dose ranges of 2 mg/kg Q3W to 10 mg/kg Q3W, 3) the lack of effect of tumor burden or indication on distribution behavior of pembrolizumab (as assessed by the population PK model) and 4) the assumption that the dynamics of pembrolizumab target engagement will not vary meaningfully with tumor type.

The choice of the 200 mg Q3W as an appropriate dose for the switch to fixed dosing is based on simulations performed using the population PK model of pembrolizumab showing that the fixed dose of 200 mg every 3 weeks will provide exposures that 1) are optimally consistent with those obtained with the 2 mg/kg dose every 3 weeks, 2) will maintain individual patient exposures in the exposure range established in melanoma as associated with maximal efficacy response and 3) will maintain individual patients exposure in the exposure range established in melanoma that are well tolerated and safe.

A fixed dose regimen will simplify the dosing regimen to be more convenient for physicians and to reduce potential for dosing errors. A fixed dosing scheme will also reduce complexity in the logistical chain at treatment facilities and reduce wastage.

#### **4.1.2 Pharmaceutical and Therapeutic Background- XL888**

Hsp90 belongs to a class of molecular chaperone proteins that help modulate cellular responses to environmental stress. In particular, Hsp90 regulates the folding, stability, and function of many so-called Hsp90 “client” proteins. Inhibition of Hsp90 is believed to cause these client proteins to adopt aberrant conformations, which are then targeted for ubiquitination and degradation by the proteasome. Hsp90 clients include wild-type and or activated forms of many important signaling proteins, such as B-Raf, c-KIT, c-MET, EGFR, human epidermal growth factor receptor 2 (HER2) and platelet-derived growth factor receptor, alpha polypeptide

(PDGFRA). Given the diversity of currently identified Hsp90 client proteins, many of which are known to be critical regulators of the immune system, the cancer microenvironment as well as cancer cell proliferation and survival, XL888 would be expected to show activity against a wide variety of human tumor types. Although human cancers are typically characterized by a wide variety of genetic alterations that collectively contribute to the transformed state, a subset of cancers appears to be particularly dependent upon single oncoproteins for their genesis, sustained proliferation, and survival. In such cancers, inactivation of the critical oncoprotein can cause rapid cell growth arrest, differentiation, or apoptosis. This phenomenon has been termed “oncogene addiction”. Importantly, a number of such “addicting” oncoproteins are also Hsp90 client proteins, and therefore cancers involving these oncoproteins are particularly promising indications for treatment by Hsp90 inhibition.

XL888 is a synthetic small molecule that binds to the ATP pocket in the N-terminus of Hsp90. It demonstrates significant activity for down-regulating Hsp90 client protein levels. These proteins include EGFR, HER2, MET, insulin-like growth factor-I receptor (IGF-IR) and other signaling kinases. Inhibitors of HSP90 have been shown in preclinical studies and in patient samples to exert anti-tumor effects as well as modulation of signaling pathways.

### **XL888 dose selection/regimen/modification**

Clinical data are available for two clinical studies with XL888. Clinical Study XL888-001 enrolled a total of 33 subjects (study completion date/database lock 22 November 2010). In the ongoing investigator sponsored Study XL888-IST1 a total of 21 subjects have received at least one dose of XL888. Safety information on SAEs is provided to 7 April 2016.

#### **XL888-001**

XL888-001 was a non-randomized, open-label, dose-escalation Phase 1 study conducted in 33 subjects to determine the MTD of XL888 in subjects with refractory solid tumors and to explore the compound’s safety, PK, and pharmacodynamics. XL888 was administered orally on an intermittent schedule. This study evaluated both a PIB formulation and a capsule formulation twice weekly, in 28-day cycles.

The age of the 33 subjects enrolled ranged from 46 to 80 years. Mean age was 64.3 years (standard deviation [SD] 9.32). Sixteen subjects (48.5%) were male, and 17 subjects (51.5%) were female. Sixteen subjects (48.5%) were aged between 45 and 65, and 17 subjects (51.5%) were aged 65 and over. The ECOG performance status (PS) of subjects at baseline was as follows: 16 subjects (48.5%) had a PS of 0; 15 subjects (45.5%) had a PS of 1; and two subjects (6.1%) had a PS of 2.

The primary disease sites for subjects in this study were 10 subjects (30.3%) with colon cancer; 3 subjects each (9.1%) each with prostate, breast, skin, or rectal cancer; 2 subjects (6.1%) each with endometrial cancer, pancreatic, or liver cancer; and 1 subject each (3.0%) with lung, parotid, submandibular, ovarian, or unknown primary cancers.

At the MTD of 135 mg capsule, the number of doses per subject ranged from eight to 31 (mean 18.7, SD 8.94). The number of days of exposure ranged from 25 to 116 (mean 65.2, SD 33.63). The mean number of cycles was 2.5 (SD 1.22). Of the six subjects in this cohort, two subjects (33.3%) completed four cycles, three subjects (50.0%) completed 2 cycles, and one subject (16.7%) completed one cycle.

The most frequently observed AEs ( $\geq 10\%$  of subjects), regardless of the relationship to XL888 are diarrhea, fatigue, nausea, decreased appetite, vomiting, abdominal pain, vision blurred, AST increased, and alkaline phosphatase increased. Most reported AEs were mild, Grade 1 to 2 severity except for four (12.1%) reports of AST elevation, 3 (9.1%) of blood alkaline phosphatase increased, and 1 (3.0%) of fatigue, all of which were Grade 3.

### **XL888-IST1**

The primary objectives of the study were to determine the MTD and recommended Phase 2 dose (RP2D) of XL888 when administered orally with vemurafenib in subjects with advanced BRAFV600 mutated melanoma and to evaluate the safety and tolerability of this combination. SixXL888 month progression-free survival (PFS), 1-year overall survival (OS) and overall response rate (ORR) by Response Evaluation Criteria in Solid Tumors version 1.1 (RECIST 1.1) were also to be assessed as secondary endpoints.

The XL888 MTD and R2PD were therefore established as 90 mg BIW (in combination with 960 mg vemurafenib BID). Ten (48%) subjects reported SAEs. Three subjects had SAEs associated with progressive disease (melanoma in situ, metastatic melanoma excision, and metastatic malignant melanoma) and two subjects each had SAEs of diarrhea, pleural effusion, pneumonia, and vomiting. All other SAE preferred terms (PTs) occurred in one subject. There were two subjects with Grade 5 events (pneumonia and metastatic malignant melanoma), both of which were assessed by the investigator as not related to study treatment.

In data presented for Study XL888-IST1 to the American Society of Clinical Oncology (ASCO) in June 2016 (Eroglu et al 2016), out of 19 evaluable subjects confirmed objective response was observed in 14 subjects (74%; 95% confidence interval [CI]: 54, 94), including two complete responses. Two subjects with PR who underwent surgical resection had a pathological CR. Median PFS was 7.4 months (95% CI: 3.7, 16.2). Estimated 1-year PFS was 40%. Median OS was 33.1 months (95% CI: 5.75, not reached).

## 4.2 Rationale

HSP90 has several effects on the immune system, cancer cells, and tumor microenvironment. **Our overall hypothesis is that the inhibition of HSP90 can modulate multiple facets of the interactions between cancer cells and immune system leading to potentiation of the immunologic response triggered by PD-1 inhibition.** This is based on the following preliminary data.

### A. Inhibition of HSP90 can promote expression of tumor antigens

A known mechanism of tumor evasion of the immune system is through loss of antigen expression and downregulation of MHC expression. Inhibition of HSP90 using different pharmacologic compounds has been shown to improve antigen in melanoma and glioma cell lines. Similarly, pharmacologic inhibition of HSP90 has been shown to improve epha2+ tumor cell recognition and T-lymphocyte recruitment through several mechanisms including increased MHC expression by tumor cells.

### B. Inhibition of HSP90 can modulate expression of PD-L1

The activation of HIF-1 $\alpha$  and JAK-STAT pathway leads to transcription and overexpression of immune suppressive proteins including PD-L1. Our group has demonstrated in vivo and in patient samples that inhibition of HSP90 results in downregulation of HIF-1 $\alpha$  and JAK-STAT in colorectal and pancreatic cancer (not published). Therefore, targeting HSP90 may modulate the expression of immune inhibitory pathways including PD-L1.

### C. Inhibition of HSP90 can affect tumor microenvironment

One of the main challenges in tumor immune therapy is the immune suppressive tumor microenvironment. The immune suppressive effects associated with the tumor microenvironment include:

1. Hypoxia, acidity and high interstitial pressures: the abnormal tumor vasculature impairs dendritic cell function, inhibits proliferation and function of T-cells and promotes accumulation of alternative activated macrophages (TAM-M2). Anti-angiogenic therapy has been shown to normalize tumor vasculature leading to improved oxygenation and reversal of hypoxia. Furthermore, normalization of tissue vasculature has been shown to improve immune function and as such would be a rational strategy to combine with immune modulators.
2. Circulating VEGF inhibits immune cell proliferation and function.
3. T cell exhaustion through chronic stimulation of tumor infiltrating lymphocytes through cytokines. Exhausted T cells have persistent and unopposed activation of proteins like PD-1, Tim-3 and LAG3. Tim3 and LAG3 have been shown to signal through activation of PI3K, Akt and NF- $\kappa$ B signaling pathways. Inhibition of these signaling pathways may potentiate the effects of PD-1 inhibitors.
4. Macrophage migration inhibitory factor (MIF) is a pro-inflammatory cytokine that has been shown to be overexpressed in the tumor micro-environment. MIF has been associated with immune suppressive effects.

**Our group has previously shown that the inhibition of HSP90 using ganetespib can modulate angiogenesis, inhibit tumor invasion, and activation of cytokines and inflammatory pathways such as NF- $\kappa$ B. In addition, we have demonstrated that HSP90 inhibition can result in downregulation of VEGF expression. MIF is a HSP90 client protein and inhibition of HSP90 has been shown to downregulate MIF.**

Furthermore, recent data reported by Proia *et.al.* demonstrate that the combination of ganetespib potentiates the antitumor effects of PD-L1 antibody (STI-A1015) in syngeneic mouse models of colorectal cancer and melanoma.

Heat shock protein 90 has a central role in modulating angiogenesis, tumor microenvironment, inflammatory signaling pathways (NF- $\kappa$ B, HIF-1 $\alpha$  and Jak-STAT), tumor antigen presentation and expression, PD-L1 expression and MIF as well as cytokine production. Inhibition of HSP90 may provide an approach to modulate the microenvironment to improve immune function and potentiate the effects of PD-1 inhibitors in patients with solid tumors. The purpose of this trial is to evaluate the safety of combining an HSP90 inhibitor with a PD-1 inhibitor and to obtain preliminary data regarding the activity of such a combination.

#### **4.2.1 Rationale for Endpoints**

- 4.2.1.1 Efficacy Endpoints:** This is a phase I trial. The primary endpoint is still toxicity. The plan is to evaluate the response rate, response duration, and progression free

survival of the patients on the trial. These endpoints will provide preliminary data in two patient subsets: patients with pancreatobiliary and other GI malignancies.

- 4.2.1.2 **Biomarker Research:** We intend in all patients to evaluate the effects of the combination on T-cell population in peripheral blood. In addition, we plan to evaluate the effects of the combination versus pembrolizumab alone in paired biopsy samples in 16 patients. These samples will be analyzed for tumor infiltrating lymphocytes, stromal/tumor markers and expression immune inhibitory molecules (PD-L1, PD-L2, PD1, etc). We anticipate to see a difference between the group treated with the combination versus the group treated with pembrolizumab alone.

## 5.0 METHODOLOGY

### 5.1 Entry Criteria

#### 5.1.1 Diagnosis/Condition for Entry into the Trial

- a. In the dose escalation phase, the trial will be open for patients with stage IV or locally advanced unresectable gastrointestinal adenocarcinomas (gastric, GEJ, cholangiocarcinoma, hepatocellular, pancreas, small intestinal tumors) who have failed at least one prior therapy. Patients with colorectal cancer must have previously received oxaliplatin, irinotecan, and a fluoropyrimidine.
- b. In the dose expansion phase, Arm A will be open for 16 patients with pancreatic adenocarcinoma. Patients must have histologic diagnosis and either locally advanced unresectable or metastatic disease that has failed at least one standard regimen. Eight patients will participate in the paired biopsy studies. Patient selected for biopsy must have a primary or metastatic non-bone site that is amenable to safe biopsy. Bone only lesions are not suitable for biopsy. These patients will provide informed consent for the paired biopsy study.
- c. In dose expansion phase, Arm B will be open for 16 patients with colorectal adenocarcinoma. Patients must have histologic diagnosis and either locally advanced unresectable or metastatic disease and have previously received oxaliplatin, irinotecan, and a fluoropyrimidine. Eight patients will participate in the paired biopsy studies. Patient selected for biopsy must have a primary or metastatic non-bone site that is amenable to safe biopsy. Bone only lesions are not suitable for biopsy. These patients will provide informed consent for the paired biopsy study.

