### **5.1.3 Subject Exclusion Criteria**

The subject must be excluded from participating in the trial if the subject:

1. Is currently participating and receiving study therapy or has participated in a study of an investigational agent and received study therapy or used an investigational device within 4 weeks of the first dose of treatment.
2. Has a diagnosis of immunodeficiency or is receiving systemic steroid therapy or any other form of immunosuppressive therapy within 7 days prior to the first dose of trial treatment.
3. Has a known history of active TB (Bacillus Tuberculosis)
4. Hypersensitivity to pembrolizumab or history of severe allergic or hypersensitivity reactions to excipients (e.g., Polyethylene glycol [PEG] 300 and Polysorbate 80)
5. Clinically significant cardiovascular disease or peripheral vascular (e.g. myocardial infarction, unstable angina within 6 months of study entry), symptomatic congestive heart failure, serious uncontrolled cardiac arrhythmia requiring medications, baseline QTc > 450 msec or previous history of QT prolongation while taking other medications
6. Other medications, or severe acute/chronic medical or psychiatric condition, or laboratory abnormality that may increase the risk associated with study participation or study drug administration, or may interfere with the interpretation of study results, and in the judgment of the investigator would make the subject inappropriate for entry into this study
7. Has had a prior anti-cancer monoclonal antibody (mAb) within 4 weeks prior to study Day 1 or who has not recovered (i.e.,  $\leq$  Grade 1 or at baseline) from adverse events due to agents administered more than 4 weeks earlier.
8. Has had prior chemotherapy, targeted small molecule therapy, or radiation therapy within 2 weeks prior to study Day 1 or who has not recovered (i.e.,  $\leq$  Grade 1 or at baseline) from adverse events due to a previously administered agent.
  - Note: Subjects with  $\leq$  Grade 2 neuropathy are an exception to this criterion and may qualify for the study.

- Note: Major surgical procedure, or significant traumatic injury within 28 days of registration or incompletely healed surgical wounds are exclusions. Minor surgical procedures such as placement of central venous device (excluding PICC line) are allowed 7 days prior to enrollment to the study.

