#### **7.1.4.1 Screening**

##### **7.1.4.1.1 Screening Period**

All subjects must sign an informed consent document prior to the initiation of any study related procedures. The informed consent document must be signed within 28 days of Cycle 1 Day 1. Screening procedures (with the exception of the scans) are to be conducted within 28 days of Cycle 1 Day 1.

- Review of study eligibility criteria
- Medical History
- Record concomitant medications taken up to 28 days prior to day 1 cycle 1
  - Vitals [temperature, heart rate (HR), blood pressure (BP) and respiratory rate (RR)]
  - Physical Examination, including height and weight
  - Ophthalmologic exam- baseline
  - ECOG Performance Status evaluation (within 10 days or less of cycle 1 day 1)
  - Laboratory Assessments
    - Hematology: hemoglobin, hematocrit, red blood cell count, white blood cell count with differential and platelet count

- Serum chemistry: sodium, potassium, chloride, bicarbonate, magnesium, calcium, phosphorus, blood urea nitrogen, creatinine, total bilirubin, LDH, total protein, ALP, ALT, AST, and albumin. Fasting triglycerides, cholesterol and glucose.
- Serum or urine pregnancy test for women of childbearing potential
- Prothrombin time (PT) and activated partial thromboplastin time (aPTT)
- Urinalysis
- Tumor markers(when applicable such as known elevated tumor markers): CEA, CA19-9, or  $\alpha$ -fetoprotein
- T3, FT4, TSH
- HIV, HBsAg, HCV RNA if clinically indicated
- 12-lead ECG
- Ophthalmologic exam
- Radiologic imaging studies to evaluate tumor status. contrast computed tomography (CT) or magnetic resonance imaging (MRI) of the chest and abdomen and pelvis. Additional imaging may be obtained as clinically indicated. Baseline scans may be done within 8 weeks prior to cycle 1 day 1.
- Baseline fresh biopsy (in selected group) will be obtained with 28 days of day1 cycle 1 and after consent is signed.

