## **8.0 STATISTICAL ANALYSIS PLAN**

### **8.1 Determination of Sample Size**

This is a 3+3 standard phase I trial design. The plan is to evaluate two dose cohorts- 45mg and 90 mg. An intermediate dose cohort (60 mg) will be evaluated only if we observe 2 or more DLT's in the 3 or 6 patients enrolled on the 90mg dose. If we observe 2 dose limiting toxicities on dose level 1, then the study will be completed with three patients (minimal number of patients). If we observe two DLT in the first three patients on dose level 1, the study will stop and the principal investigator will discuss at that point whether a lower dose level of XL888 should be tested. If we do not observe any dose limiting toxicities the study will require 9 patients. If we observe one dose limiting toxicity per dose level (maximum number of patient), then the study would require 18 patients. Therefore the phase part sample size can range from 3 to 18 patients. Expansion phase will be started once the recommended phase II dose (RP2D) is determined. Given minimal activity of checkpoint inhibitors in colorectal and pancreatic cancer, an overall response rate of the combination of PD-1 plus HSP90 inhibitor of 20% would be considered clinically significant. With an alpha of 0.1, and power of 80% (relaxed due to the pilot preliminary nature of this proposal) a total of 16 patients should be sufficient to make this determination. We will also obtain biologic endpoints with the paired biopsy samples that can help further develop the combination and understand its role in GI cancers. We plan to enroll 32 patients on the RP2D level with 16 patients per cohort (pancreas and colorectal cancer). Patients in the expansion phase will be assigned to treatment arms by PI (MK-3475 or MK-3475 plus XL-888). After the first 3 weeks all patients will receive the combination therapy. There is no planned comparison between the two arms. The aim of the expansion phase is to confirm the safety profile and tolerability of the regimen in patients with pancreatic and colorectal cancer.

The total number of patients will range from 38 to 50 patients.

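### Arm B asks colorectal patients only for prior receipt of three drugs, and no criterion requires progression on the latest regimen, so controlled disease can enter and lengthen PFS or, with an early baseline scan, add responses

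*Combined protocol and SAP*

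**What the plan says.** Prior-therapy wording, all in Section 5.1.1:

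- **Arm B, colorectal (c):** "locally advanced unresectable or metastatic disease and have previously received oxaliplatin, irinotecan, and a fluoropyrimidine".
- **Arm A, pancreatic (b):** "either locally advanced unresectable or metastatic disease that has failed at least one standard regimen".
- **Escalation (a):** patients with a bracketed list of gastrointestinal tumours "who have failed at least one prior therapy". Colorectal cancer is not in that list. A separate sentence asks colorectal patients for prior receipt of the same three drugs as in Arm B.

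Section 5.1.2 adds measurable disease by RECIST 1.1 but nothing about progression. In Section 5.1.3, exclusion 8 rules out a patient who "Has had prior chemotherapy, targeted small molecule therapy, or radiation therapy within 2 weeks prior to study Day 1", and a note under it allows neuropathy of Grade 2 or lower. Exclusion 7 rules out one who "Has had a prior anti-cancer monoclonal antibody (mAb) within 4 weeks prior to study Day 1". No exclusion concerns whether the study cancer is progressing.

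On imaging, Section 7.1.4.1.1 states "Baseline scans may be done within 8 weeks prior to cycle 1 day 1", and the flow chart in Section 6.1 gives the same allowance. The first on-study scan falls between days 15 and 21 of cycle 3 (Section 7.1.4.4).

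On use of the data, Section 3.2 makes response rate, response duration and PFS secondary and preliminary. Section 8.1 says that "an overall response rate of the combination of PD-1 plus HSP90 inhibitor of 20% would be considered clinically significant" and derives 16 patients from it with alpha 0.1 and 80% power. Section 8.3 rules out formal testing, and Section 1.0 lists no control.

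**The concern.** In a single-arm cohort, the credit given to the study drugs depends on patients having disease that is growing, or at least not still under the influence of the last treatment, when they start. The criteria do not secure this. A colorectal patient who has had all three drugs, is stable or responding, and stops because of mild neuropathy meets the prior-therapy and washout criteria about two weeks after the last chemotherapy dose.

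Two effects follow. Entering with controlled disease can lengthen PFS whatever the study drugs do. And if the baseline scan was taken before the last chemotherapy doses, shrinkage from those doses appears at the first on-study scan as a change from baseline. With no control group, neither effect can be separated from activity of the combination, and a 16-patient arm is sensitive to one or two such patients.

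**Working it through.** **1. Is progression required anywhere?** Arm B asks for receipt of drugs. Escalation has a received-only sentence for colorectal patients. Arm A asks for failure of at least one regimen, which a patient meets after failing first-line treatment even if second-line treatment is controlling the disease. Sections 5.1.2 and 5.1.3 add nothing. No cohort therefore has a criterion that ensures progression on the most recent regimen.

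**2. Can the baseline scan predate the last chemotherapy?** The scan may be 8 weeks (56 days) before Day 1, and chemotherapy may end about 14 days before it. 56 − 14 = 42 days, so up to six weeks of chemotherapy can follow the baseline scan. For an antibody the figure is 56 − 28 = 28 days. The first on-study scan falls on study day 2 × 21 + 15 = 57 to 2 × 21 + 21 = 63. Shrinkage in the interval before Day 1 would be counted by then.

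**3. Weight of one response.** 1/16 = 6.25 percentage points. The benchmark is 0.20 × 16 = 3.2 responses, so one carried-over response is 1/3.2 = 31% of it.

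**4. The plan's figure of 16.** Section 8.1 gives no null rate, sidedness or decision rule, so 16 cannot be confirmed from its inputs. It can be approached by assumption. With an exact binomial rule of at least 2 responses in 16:

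- power at 20% is 85.9%;
- one-sided alpha is 4.0% at a null rate of 2%, 8.2% at 3% and 18.9% at 5%; it stays within 10% only up to a null rate of about 3.37%.

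A rule of at least 3 in 16 has only 64.8% power. The smallest exact sample size is 14 at null rates of 2–3% and 21 at 5%. The normal approximation at 5% gives 17.

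**5. Illustration for response (assumed inputs).** Take the rule of at least 2 in 16, null rates of 2% and 3%, and no drug effect. Each non-progressing entrant responds with probability p0 + (1 − p0)c, where c is the chance of a carry-over response.

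| Situation | p0 = 2% | p0 = 3% |
|---|---|---|
| No carry-over | 4.0% | 8.2% |
| 4 of 16 non-progressing, c = 10% | 15.5% | 21.3% |
| 4 of 16 non-progressing, c = 20% | 30.4% | 36.5% |
| One certain carry-over response, 1 − (1 − p0)^15 | 26.1% | 36.7% |

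Entries are the chance of meeting the assumed rule by error.

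**6. Illustration for PFS (assumed inputs).** Assume exponential times with a median of 2 months in progressing entrants and 4 months in the others, who make up a share f: S(t) = (1 − f) × 0.5^(t/2) + f × 0.5^(t/4). At f = 0.25, S(6) = 0.75 × 0.125 + 0.25 × 0.354 = 18.2%, against 12.5% at f = 0. The median moves from 2.0 to 2.3 months. If the second median is varied from 3 to 6 months, S(6) runs from 15.6% to 21.9% and the median from 2.2 to 2.5 months.

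**The case against.** **Response is measured from the study baseline.** Stable disease is not a response, and shrinkage already present on the baseline scan is not counted again. This stands: inflation of the response rate depends mainly on a scan that predates the last chemotherapy. The PFS effect does not need that condition.

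**The stakes are limited.** Activity is secondary and preliminary, there is no formal test, and Section 8.1 states the aim of the expansion as confirming safety and tolerability. This also stands, and it keeps the point modest. Section 8.1 nevertheless justifies the 16 patients by a 20% response rate, so the rate will be read against that figure.

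**Patients who have had all three drugs have often progressed.** That may be so, but the criterion does not require it.

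Three stronger readings are tempting, and the documents do not support them:

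- *The escalation phase would reject the same patient.* Section 5.1.1(a) gives colorectal patients the same received-only sentence and leaves them out of the list to which failure is attached. Whether failure applies to them is unclear.
- *Arm A is refractory while Arm B is merely exposed.* Failing at least one regimen does not mean progressing at entry, and the same two-week washout applies to Arm A.
- *Progression dates are already collected.* Section 7.1.1.5 asks for disease status and prior treatments without naming such a date.

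**Conclusion.** The gap is real and worth closing, but it is a cheap improvement and not a flaw that undermines the trial's primary objective. The written criteria allow colorectal patients with controlled disease to enter Arm B, and comparable patients can enter the other cohorts. PFS can be lengthened directly. Response can be inflated where the baseline scan precedes the last chemotherapy dose, at 6.25 points per response in a 16-patient arm. The documents do not indicate how many such patients would enrol, so the criteria show a possible bias and not its size. The error rates and PFS shifts above rest on an assumed decision rule, null rates, carry-over chances and medians. They show how sensitive 16 patients are and do not predict the result.

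**What to change.** - In Section 5.1.1(c), keep the three-drug requirement and add documented radiographic progression on or after the most recent regimen, or after stopping that regimen for intolerance.
- Use the same progression wording in 5.1.1(a) and (b), and make clear how (a) applies to colorectal patients.
- Record the date of that progression.
- In Sections 6.1 and 7.1.4.1.1, require the baseline scan to follow the last dose of prior therapy. The progression criterion alone would leave the eight-week scan window able to capture chemotherapy effect.

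The sample size is unchanged. The cost is slightly narrower accrual, since some patients without documented progression would have to wait or be turned away, some repeat baseline scans, and possibly one added data field.
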